5.5 Efficacy in the Maximal Use Arm

All efficacy data collected from subjects in the maximal use arm will be listed in by-subject data listings. No formal comparison will be made with the results of the main Phase 3 study.

6.0 PHARMACOKINETICS/PHARMACODYNAMICS ANALYSIS

Pharmacokinetic and pharmacodynamic analyses are outside of the scope of this SAP. Details will be provided in a separate PK data analysis plan.

7.0 SAFETY ANALYSIS

All analyses in this section will be performed using the Safety Population and presented as described in Section 3.11.3, unless otherwise indicated.

7.1 Study Drug Exposure and Compliance

All study drug exposure and compliance analyses will be performed on primary dosing (Periods 1 & 2) alone, open-label dosing (Period 3) alone, and all periods combined, unless otherwise noted.

For all parameters below, the following rules apply:

- Primary dosing is considered as the time where study drug was applied to complete requirements of Periods 1 & 2
 - The date of first dose of primary dosing is the date where the first dose was administered in Period 1
 - The date last dose of primary dosing is the date where the last dose was administered in Period 2
- Open-label dosing is considered as the time where study drug was applied to complete requirements of Period 3
 - The date of first dose of open-label dosing is the date where the first dose was administered in Period 3
 - The date of last dose of open-label dosing is the date where the last dose was administered in Period 3
- Combined dosing consists of both primary and open-label dosing.
 - The date of first dose of combined dosing is the date where the first dose was administered in Period 1
 - The date of last dose of combined dosing is the date where the last dose was administered in Period 3

Overall duration of study drug exposure will be calculated as the number of days subjects were administered study drug, as below, and will be summarized using descriptive statistics.

$$\text{Duration (days)} = (\text{date of last dose} - \text{date of first dose}) + 1$$

Duration of treatment, defined as the number of days dosed, will also be provided for comparison.

Dosing compliance will be summarized using descriptive statistics, and is defined as

$$\text{Dosing Compliance (\%)} = \frac{\text{Number of Actual Doses Applied}}{\text{Number of Expected Doses Applied}}$$

The number of expected doses applied will be dictated by a subject's status on the study. Specifically, doses that would be expected will not contribute to the denominator if they occur after a subject has discontinued from the study.

The number of subjects and percentages of subjects with <50% versus ≥50%, and <80% versus ≥80% dosing compliance will be presented. For subjects with missing doses, the number and percentages will be provided, along with the reasons why the doses were missed.

The total amount of study drug applied (in grams) will be summarized using descriptive statistics based on the data provided by the weighing of study drug tubes. A full – unused – tube's weight averages 101g. Any returned tube weighing more than 101g will be set to 101g. The assumption that the amount of study drug that was removed from the tube is equivalent to the amount of study drug applied will be used.

Additionally, actual dose intensity (g/day), defined as the ratio of total drug applied and the duration of study drug exposure will be summarized using descriptive statistics.

Data collected in the eDiary will be summarized using descriptive statistics, as applicable.

Specifically for Period 1 (the first 21 days), the number of Cetaphil applications per subject will be provided using descriptive statistics.

Both observed exposure data (including eDiary) and derived exposure parameters will be provided in by-subject data listings.

In addition to the Safety Population, all exposure analyses will be performed on the ITT population as well.

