- Screening assessments (except for genetic testing) may be performed up to 90 days prior to Visit 2 (Baseline) for those qualified subjects who are eligible to enroll in the study but require washout of medications prior to enrolling into the Treatment Phase of the study. Genetic confirmation should be obtained prior to conducting additional eligibility assessments in the Screening period. There is no window for obtaining genetic confirmation, it can be obtained at any time following consent and with no restriction until Visit 2 (Baseline). The Screening visit may be split into two visits to accommodate the genetics testing first, following by all other screening assessments.
- Visit 6 (day 84/Week 12) is the EOS visit for subjects who are not eligible to continue maintenance treatment.
- Subjects at the end of the study or subjects discontinued from the study at any time will be followed-up for additional 2 weeks for AEs.
- For subjects who require genetic testing, or a washout period related to exclusionary medications, reaffirm these subjects meet all protocol requirements at Visit 2 (Baseline).

- f. Examination will include head and neck, dermatologic, cardiovascular, respiratory, gastrointestinal (abdomen), and gross motor and gait assessments. Additional examinations will be conducted at Visit 2 (Baseline) to identify any changes since Screening, at Visit 6 and Visit 9 (EOS) to assess changes throughout the study. Abnormalities at Visit 1 (Screening) and Visit 2 (Baseline) will be recorded as medical history. Any new or worsening abnormality at all subsequent visits will be recorded as AEs.
- g. If there are less than two weeks between Visit 1 (Screening) and Visit 2 (Baseline), the physical examination at the Visit 2 (Baseline) includes only a dermatological assessment.
- h. Subjects who meet all inclusion criteria and none of the exclusion criteria will be randomized at Baseline (2:1 ratio) to either the TMB-001 0.05% or the vehicle treatment group, stratified by age and CI subtype.
- i. At Week 12, eligible subjects in the TMB-001 0.05% treatment group will be randomized (1:1 ratio) to either TMB-001 0.05% QD or BID maintenance treatment.

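### SAP 7.1 takes the last dose of primary dosing from Period 2 and of combined dosing from Period 3, so duration and dose intensity are undefined for subjects with no dose in that period

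*SAP*

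**What the plan says.** SAP 7.1 analyses exposure for primary dosing (Periods 1 and 2), open-label dosing (Period 3) and all periods combined. It introduces its date rules with "For all parameters below, the following rules apply". For primary dosing, "The date of first dose of primary dosing is the date where the first dose was administered in Period 1" and "The date last dose of primary dosing is the date where the last dose was administered in Period 2". For combined dosing, the first dose is again taken from Period 1, and "The date of last dose of combined dosing is the date where the last dose was administered in Period 3".

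The duration rule reads "Overall duration of study drug exposure will be calculated as the number of days subjects were administered study drug, as below", followed by the formula: date of last dose minus date of first dose, plus 1. The same section adds "actual dose intensity (g/day), defined as the ratio of total drug applied and the duration of study drug exposure". It also says "Duration of treatment, defined as the number of days dosed, will also be provided for comparison".

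SAP 7.0 places these summaries on the Safety Population (SAP 2.3: at least one dose received), and SAP 7.1 repeats them on the ITT population.

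Exit at Week 12 is part of the design. Under Protocol 4.1 and SAP 1.3.1, TMB-001 subjects with less than a 1-point IGA reduction are discontinued, as are vehicle subjects with a reduction of 1 point or more. A footnote to Protocol Table 1 confirms it: "Visit 6 (day 84/Week 12) is the EOS visit for subjects who are not eligible to continue maintenance treatment". Protocol 4.4 counts these subjects as having completed the study.

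**The concern.** The formula needs both dates. A subject who stops during the first three weeks has no Period 2 dose, so the primary end date does not exist. A subject with no Period 3 dose has no combined end date. The second group includes earlier dropouts, vehicle subjects eligible to cross over who do not, and everyone discontinued at Week 12 by rule. All of them received study treatment and belong in the populations that SAP 7.0 and 7.1 name.

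If the undefined values become missing, the combined table no longer describes the treated population. SAP 3.11.3 puts safety columns by initial randomization. The TMB-001 column would then keep only subjects with at least a 1-point IGA improvement who continued, and the vehicle column only subjects without that improvement who crossed over. The two columns would be selected in opposite directions on response. Short exposures would be removed from the mean, and dose intensity would be summarized in the same selected group.

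**Working it through.** The documents state no exposure figure to reproduce, so the check applies the SAP formula to each disposition path and then sizes the effect under stated assumptions.

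**Paths under the literal rule**

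| Path | Primary duration | Combined duration |
|---|---|---|
| Stops in Period 1 | undefined | undefined |
| Stops in Period 2 | defined | undefined |
| Leaves at Week 12 | defined | undefined |
| Doses in Period 3 | defined | defined |

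**Inputs**
- From the documents: Period 1 lasts 21 days, Week 12 is Day 84 and Week 24 is Day 168. Arm sizes are 74 TMB-001 (SAP 1.3.2) and 110 - 74 = 36 vehicle.
- Assumed: dropout before Week 12 of 0% or 15%, uniform over 84 days. The 15% is borrowed from SAP 1.3.3, where it also covers non-evaluable subjects.
- Assumed: a share p of Week 12 completers enters Period 3, varied from 50% to 100% because no document gives it. All entrants complete Period 3.

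**Primary duration, 15% dropout**
- Stops in Period 1: 0.15 x 21/84 = 3.75%, mean 10.5 days. That is 0.0375 x 74 = about 2.8 TMB-001 subjects.
- Stops in Period 2: 11.25%, mean (21 + 84)/2 = 52.5 days. Completers: 85% at 84 days.
- Mean using the actual last dose: 0.0375 x 10.5 + 0.1125 x 52.5 + 0.85 x 84 = 77.7 days.
- Literal mean, Period 1 stoppers dropped: (0.1125 x 52.5 + 0.85 x 84)/0.9625 = 80.3 days.
- Overstatement: 80.3/77.7 - 1 = about 3%.

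**Combined duration**
- With 15% dropout, the undefined share is 1 - 0.85p. The actual mean is 0.0375 x 10.5 + 0.1125 x 52.5 + 0.85 x [84(1 - p) + 168p] = 6.3 + 71.4(1 + p).
- With no dropout, the undefined share is 1 - p and the actual mean is 84(1 + p).
- The literal mean is 168 days throughout, since only Period 3 entrants remain. Overstatement is 168/actual mean - 1.

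| Dropout | p | Undefined | Of 74 TMB-001 | Actual mean (days) | Overstatement |
|---|---|---|---|---|---|
| 15% | 50% | 57.5% | about 43 | 113.4 | 48% |
| 15% | 70% | 40.5% | 30 | 127.7 | 32% |
| 15% | 90% | 23.5% | about 17 | 142.0 | 18% |
| 15% | 100% | 15% | about 11 | 149.1 | 13% |
| 0% | 50% | 50% | 37 | 126.0 | 33% |
| 0% | 70% | 30% | about 22 | 142.8 | 18% |
| 0% | 90% | 10% | about 7 | 159.6 | 5% |
| 0% | 100% | 0% | 0 | 168.0 | 0% |

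The percentages apply to either arm at the same p, though p may well differ between arms. If some entrants leave Period 3 early, both means fall and the relative gap narrows.

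**Dose intensity.** The duration is its denominator, so it is undefined for the same subjects. The documents give nothing from which to tell whether those subjects used more or less ointment per day, so the direction of any bias is unknown.

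**Search for a repair elsewhere.** The only discontinuation rule in SAP 7.1 concerns expected doses in the compliance denominator. The SAP addendum does not change 7.1 and leaves SAP Version 3.0 in force unless it says otherwise.

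**The case against.** The strongest reply is that the harm depends on programming. SAP 7.1 describes duration as days on which drug was administered and says combined dosing comprises primary and open-label dosing. With the Safety Population named in SAP 7.0, a sensible programmer could read the period-specific dates as describing a subject who completes each period, and use the actual last dose for everyone else. That stands as a limit on the claim: the overstatement follows only if undefined values are treated as missing. It does not remove the defect, because the date rules are explicit, apply to every parameter in the section, and have no written fallback.

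A reader might also infer that early stoppers vanish from the exposure reporting altogether, or that adverse event rates are distorted. The documents do not support either. Days dosed, grams applied from tube weights, compliance and the by-subject listings of observed exposure do not need these end dates. Week 12 leavers keep a defined primary duration. The exposure-adjusted incidence rates in addendum section 6.0 have their own time at risk, running to the first event or the last visit. SAP 3.2.1 reports the number of subjects with each continuous summary, so a reduced count would be visible.

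Finally, the primary-dosing part is minor. Protocol 7.1 handles skin reactions largely by area-specific interruption and aims to keep subjects in the study, so complete stops in Period 1 may be few.

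**Conclusion.** The rule is wrong as written: for combined dosing it yields no duration and no dose intensity for a group that the design itself creates. If undefined values are set to missing, mean combined duration is overstated by about 13-48% with 15% dropout and 50-100% of completers entering Period 3, or about 5-33% with no dropout and 50-90% entering. These ranges rest on an unstated continuation share, uniform dropout and full completion of Period 3. It would be tempting to quote one narrow figure, but the documents do not support one. The effect on primary duration is about 3%.

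A reader might also conclude that dose intensity is inflated. Only selection can be shown there, not direction. These are descriptive summaries, and no efficacy analysis or hypothesis test uses them. The point merits a correction to the SAP and does not threaten the trial's conclusions.

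**What to change.** In SAP 7.1, define the last dose of primary dosing as the last application in Period 1 or Period 2, whichever is later, and the last dose of combined dosing as the last application in any period. Every treated subject then has a duration for primary and combined dosing, and a dose intensity wherever tube weights are available. The open-label definition can stay, since it concerns only subjects dosed in Period 3.

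The cost is two sentences of SAP text and a small programming change. No new data are needed and no clinical rule changes. The only downside is a lower reported mean duration.

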7.1.1 Study Drug Exposure in the Maximal Use Arm

Study drug information will be provided in a by-subject data listing. Data collected from the Electronic Data Capture (EDC) as well as the subject eDiary will be provided.

Study drug compliance during the pharmacokinetic sampling period (Days 1 through 14) will be computed and presented in the listing.

7.2 Adverse Events

All adverse events (AEs) will be coded using the MedDRA v25.0 coding system and displayed in tables and data listings using system organ class (SOC) and preferred term. Missing and partial dates will be handled as described in Section 3.9.2.

Analyses of AEs will be performed for those events that are considered treatment-emergent, where treatment-emergent is defined as any AE with onset after the first application of study drug through 30 days after the last study drug application, or any event that was present at baseline but worsened in intensity or was subsequently considered drug-related through 30 days after the last study drug application.

Adverse events will be summarized by subject incidence rates; therefore, in any tabulation, a subject contributes only once to the count for a given AE in both SOC and preferred term. The table will be sorted by descending frequency, based on the overall column of the data presentation.

Adverse events will be reported separately by event type; reporting of SOCs and preferred term will be as described above.

The number and percentage of subjects with any treatment-emergent adverse event (TEAE), with any TEAE assessed as related to study drug (possibly or probably), with any serious TEAE, any non-serious TEAE, with any serious TEAE potentially related to study drug, any non-serious TEAE potentially related to study drug, with any common (occurring in $\geq 5\%$ of subjects) TEAE, or with any TEAE leading to study drug withdrawal will be provided. Additional tabulations will be provided for TEAEs by maximum severity, and TEAEs by strongest relationship to study drug.

All analyses above will be performed using both data presentations described in Section 3.9.3, where TEAEs will contribute to each summary only if they began in the corresponding period. For example, a TEAE starting during Periods 1 or 2 will be reported using the primary safety data presentation, and a TEAE starting during Period 3 will be reported using the open-label dosing data presentation.

Additionally, the proportion of subjects experiencing a TEAE through Week 12 will be reported along with exact binomial 95% confidence intervals, using the primary safety data presentation. The proportion of subjects experiencing a TEAE through Week 24 will be reported along with exact binomial 95% confidence intervals, using the open-label dosing data presentation.

All AEs occurring on-study will be listed in subject data listings. Listings will also be provided for the following: study drug related TEAEs, serious TEAEs, study drug related serious TEAEs, TEAEs leading to study drug withdrawal, and deaths.

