
The Investigator will make an assessment of intensity for each AE and SAE reported during the study and assign it to 1 of the following categories:
 
Mild: An event that is easily tolerated by the subject, causing minimal discomfort and not interfering with everyday activities.Moderate: An event that causes sufficient discomfort and interferes with normal everyday activities.Severe: An event that prevents normal everyday activities. An AE that is assessed as severe should not be confused with a SAE. Severe is a category utilized for rating the intensity of an event; and both AEs and SAEs can be assessed as severe. 
An event is defined as 'serious' when it meets at least 1 of the predefined outcomes as described in the definition of an SAE, NOT when it is rated as severe.

Assessment of Causality

The Investigator is obligated to assess the relationship between study treatment and each occurrence of each AE/SAE. The AE must be characterized as unrelated, unlikely to be related, possibly related, probably related, or unknown (unable to judge).
"Probably related" conveys that there are facts, evidence, and/or arguments to suggest a causal relationship, rather than a relationship cannot be ruled out."Possibly related" suggests that the association of the AE with the study treatment is unknown; however, the AE is not reasonably supported by other conditions."Unlikely to be related" suggests that only a remote connection exists between the study treatment and the AE. Other conditions, including chronic illness, progression or expression of the disease state or reaction to concomitant therapy, appear to explain the reported AE."Unrelated" is used if there is not a reasonable possibility that the study treatment caused the AE.All efforts should be made to classify the AE according to the above categories. The category "unknown" (unable to judge) may be used only if the causality is not assessable, e.g., because of insufficient evidence, conflicting evidence, conflicting data, or poor documentation.The Investigator will use clinical judgment to determine the relationship.

- Alternative causes, such as underlying disease(s), concomitant therapy, and other risk factors, as well as the temporal relationship of the event to study treatment administration will be considered and investigated.

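### SAP 7.2 counts a TEAE as related only if rated possibly or probably related, and gives no place to the protocol's fifth rating, unknown

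*SAP*

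**What the plan says.** Protocol Appendix 3 (Assessment of Causality) sets a five-level rating: "The AE must be characterized as unrelated, unlikely to be related, possibly related, probably related, or unknown (unable to judge". The last level is restricted; it "may be used only if the causality is not assessable", for instance when evidence is insufficient or conflicting or documentation is poor. The same appendix explains that a rating of *possibly related* "suggests that the association of the AE with the study treatment is unknown", with the event not reasonably supported by other conditions.

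SAP 7.2 turns this scale into tables. Its overview counts subjects "with any TEAE assessed as related to study drug (possibly or probably" related. For serious events it changes the term and counts subjects "with any serious TEAE potentially related to study drug", with a matching count for non-serious events; *potentially related* is not defined. It also plans a table of "TEAEs by strongest relationship to study drug". The listings include "study drug related TEAEs, serious TEAEs, study drug related serious TEAEs", again without a definition of related. Separately, "All AEs occurring on-study will be listed in subject data listings".

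**The concern.** The analysis rule places two of the five ratings in the related class. Two others, unrelated and unlikely, fall outside it in an obvious way. The fifth, *unknown*, is not addressed, and the literal effect is to leave it out. This is the rating used when the investigator could not exclude a drug effect because the information was inadequate, so the reported related rate can be understated where doubt is greatest.

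The dividing line is also thin. By the protocol's own description, *possibly related* is a rating of uncertain association. One kind of uncertainty is counted and its neighbour is not, and no reason is given.

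If the SAP does not settle this, the choice falls to whoever programs the tables. Under SAP 3.1 that may happen around a Week 12 topline analysis that can include safety data.

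**Working it through.** The plan gives no figure to reproduce, so the check is mainly a comparison of text.

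**Step 1. Follow each rating through the SAP 7.2 outputs.**

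| Appendix 3 rating | Any related TEAE | Potentially related serious and non-serious counts | Study drug related listings | Strongest-relationship table | Overall, serious and maximum-severity tables; all-AE listing |
|---|---|---|---|---|---|
| Probably | in | in | in | ranked | in |
| Possibly | in | in | in | ranked | in |
| Unlikely | out | probably out | probably out | ranked | in |
| Unrelated | out | out | out | ranked | in |
| Unknown | out, by literal reading | probably out; term undefined | probably out; term undefined | no rank given | in |

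The serious table and the serious-TEAE listing apply when the event is serious. Only the first *out* for *unknown* follows directly from the wording. The next two entries are the likely reading, because nothing suggests a different meaning, but the SAP does not state them.

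**Step 2. Look for a rule elsewhere that fills the gap.** SAP 3.9.2 (Adverse Event Data) handles partial dates only. Section 6.0 of the SAP addendum adds exposure-adjusted incidence rates to all AE tables and does not address causality. Protocol 10.3.1.2 asks for summaries by relationship without grouping the ratings, and SAP 1.2 says that the SAP supersedes the protocol's analysis plan. No rule was found.

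**Step 3. Test the strongest-relationship table.** Unrelated, unlikely, possibly and probably form an ordered scale, and *unknown* is not on it. A subject with one *unlikely* and one *unknown* event therefore has no defined strongest relationship. This gap remains however *related* is read.

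**Step 4. Scale of the effect.** Inputs: 110 subjects randomized 2:1 (SAP 1.3.3), and up to 74 TMB-001 subjects for re-randomization (SAP 1.3.2).

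- Arm sizes: 110 × 2/3 = 73.3 and 110 × 1/3 = 36.7, so 73 to 74 on TMB-001 and 36 to 37 on vehicle.
- Change in the related rate for each subject whose only candidate related event is *unknown* = 1/n.
- TMB-001: 1/74 = 1.35% and 1/73 = 1.37%, about 1.4 points.
- Vehicle: 1/37 = 2.70% and 1/36 = 2.78%, so 2.7 to 2.8 points.
- Illustration with three such TMB-001 subjects: 3/74 or 3/73, about 4.1 points.

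The number of *unknown* ratings is not given, so the total effect cannot be computed. The exposure-adjusted rate for related TEAEs would move too. Such a subject leaves the numerator and contributes time at risk up to the last visit instead of up to event onset.

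**The case against.** The strongest reply is that the SAP is silent and that silence is not a harmful rule. Much of this stands.

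- A reader might infer that the SAP classes *unknown* as unrelated. It does not say so, and its overview has no unrelated row. The literal effect is absence from the related numerator.
- A reader might infer that *unknown* serious events are excluded by rule from the related-serious count. The parenthesis naming possibly and probably is attached only to the any-related count. Exclusion from the serious count rests on an undefined term and is an inference.
- A reader might infer that an unassessable serious event could go unreported. It would still be in the serious-TEAE count and listing, the maximum-severity table and the all-AE listing, and a fatal one would be in the deaths listing. At most, a related-serious cell would miss it.
- The safety endpoints in SAP 1.4.5 are local skin reactions, TEAEs of any cause and confirmed allergic contact dermatitis. None compares drug-related events. One clause of the treatment-emergent definition does ask whether an event present at baseline was later considered drug-related, but that is a narrow route and does not make any endpoint depend on how *unknown* is grouped in the tables.
- The protocol asks investigators to make every effort to use the other categories and requires a causality assessment before an SAE is first transmitted. Few events may be affected.
- The rule applies equally to both blinded arms, and nothing in the documents shows that it biases the comparison.

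The reply does not remove the main point. A mandatory five-level scale is analysed with a definition that names two levels, and one level has no stated place in the related count, the related listings or the ranking. Showing *unknown* in its own row would be a fair alternative to ranking it with *possibly*; the documents do not require either.

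**Conclusion.** The point holds in a limited form. Read literally, SAP 7.2 omits *unknown* events from the related-TEAE count. It probably omits them from the related serious and non-serious counts and the related listings as well, and it leaves them without a rank in the strongest-relationship table.

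The size is about 1.4 points on TMB-001, or 2.7 to 2.8 points on vehicle, per affected subject. This assumes the planned arm sizes and that the *unknown* event is the subject's only candidate related event. The number of such subjects is not known and may be zero.

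The consequence is a related rate that could be somewhat too low and a table that cannot be programmed without an unstated choice. The documents do not support a conclusion that safety events would be hidden or that a safety endpoint is compromised. The case for the change is that it is cheap and errs on the cautious side.

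**What to change.** Change SAP 7.2 only:

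1. Define *related* once, as probably, possibly or unknown.
2. Use that single term for every related and related-serious count and listing, in place of *potentially related*.
3. In the strongest-relationship table, rank *unknown* with *possibly*, or give it its own row.
4. Footnote the number of *unknown* events so that the narrower count can be recovered.

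SAP 7.2.2 needs no change: it provides by-subject listings for the maximal use arm and contains no related count.

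The cost is a sentence or two of SAP text and a table footnote. The downside is a related-TEAE rate that may be slightly higher. Only tabulation changes; investigator ratings, SAE reporting and clinical management are unaffected.
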